Study Protocol

Official title of the study: Arteriovenous Fistula Cannulation Practices and Dialysis Adequacy

NCT number: NCT04270292

Date of document: 20 April, 2020

Objective: The aim of this study was to investigate the effect of the cannulation technique used during needle insertion into the arteriovenous fistula (AVF), the direction of the fistula needle, the rotation of the needle, the AVF insertion area, and whether the artery and vein needle are on the same vascular line on the adequacy of the hemodialysis (HD).

Design: Descriptive and cross-sectional study

Methods: The study was conducted in accordance with the Declaration of Helsinki. The approval of the local ethics committee approval (Meeting no: 08/042019, Decision no: P0139R00), permission from the institutions where the study was conducted, and the verbal consent of the patients were obtained.

This study was conducted between May and December 2019 at the a total of four HD centers, including one private dialysis center, one private hospital and two state hospitals in two provinces. The study sample consisted of 164 patients who had received HD treatment with an AVF for at least six months, at three days a week and four hours a day, were aged 18 years or older, had no problem communicating, and volunteered to participate in the study. All patients were treated with a high-flux synthetic type dialyzer at the dialysis unit where the study was conducted. The same dialysate solution was used for each session with a dialysate temperature of 36°C, a standard bicarbonate concentration 30-35 mmol/l, a dialysate flow rate 500 ml/minute and a pump speed 300-450 ml/minute. All needles placed into the AVF were of the back eye type. A semi-structured questionnaire form developed by the researchers as a

result of a literature survey was used to collect the data. The form included questions on the patients' socio-demographic and clinical data and AVF cannulation. The Kt/V and urea reduction rate (URR) that were used to evaluate dialysis adequacy were regularly evaluated at the HD centers every month and recorded in the patient's chart. The mean three-month Kt /V and URR values starting from the date the study was started were calculated by the researchers and entered into the data form. The questionnaire was then completed by the researchers interviewing the patients with the face-to-face method during the second hour of HD treatment. Completing the forms took about 5 minutes. STROBE check-list was used for reporting the study.

Statistical Analysis Plan

Official title of the study: Arteriovenous Fistula Cannulation Practices and Dialysis Adequacy

NCT number: NCT04270292

Date of document: 20 April, 2020

Outcome measures

Number of fistula needle direction: The hemodialysis nurse who cannulate the patient's fistula fill the data form. There is two options about fistula direction as antegrade or retrograde.

Number of cannulation method: The hemodialysis nurse who cannulate the patient's fistula fill the data form. There is three options about cannulation method as puncture, buttonhole, and rope ladder methods.

Number of fistula needle rotated: The researchers look to the fistula needle while it inserts to the fistula. There is two options as needle rotation is yes or no.

Number of arterial and venous needle been on the same line: The researchers look to the arterial and venous line whether they are the same venous line.

Results

	Title: Number of Fistula Needle Direction						
Description: The hemodial		is nurse who cannulate the patient's fistula fill the da					
Time	Frame: up to 12 weeks						
-	▼ Outcome Measure Data 🛛 🗸						
•	Analysis Population Description						
	Arm/Group Title	e Arteriovenous Fistula Cannulation Group					
	Arm/Group Description	: The cannulation practices' of patie					
	Overall Number o Participants Analyzed						
	Measure Type: Count o Participant Unit of Measure: participant	s					
Ro	w Title						
	Antegrade direction	n 72 43.9%					
	Retrograde direction	92 56.1%					

Title: Number of Cann	ulation Method				
Description: The hemodialysis	scription: The hemodialysis nurse who cannulate the patient's fistula fill the da				
Time Frame: up to 12 weeks					
▼ Outcome Measure Data					
 Analysis Population Description 					
Arm/Group Title	Arteriovenous Fistula Cannulation Group				
Arm/Group Description:	The cannulation practices' of patie				
Overall Number of Participants Analyzed	164				
Measure Type: Count of Participants Unit of Measure: participants					
Row Title					
Area puncture	87	53.05%			
Rope ladder	54	32.93%			
Buttunhole	23	14.02%			
Buttunhole	23	14.02%			

Title: Number of Fistula Needle Rotated					
Description: The researchers look to the fistula needle while it inserts to the fis					
Time Frame: up to 12 weeks					
▼ Outcome Measure Data 🛛 🗸					
Analysis Population Description					
Arm/Group Title	Arteriovenous Fistula Cannulation Group				
	The cannulation practices' of patie				
Overall Number of Participants Analyzed	164				
Measure Type: Count of Participants Unit of Measure: participants					
Row Title					
Yes	104	63.41%			
No	60	36.59%			

Title:	Number of Arteria	al and Venous Needle Been on the Same Line			
Description:					
Time Frame:	Time Frame: up to 12 weeks				
▼ Outcome Measure Data					
Analysis P	otion				
	Arm/Group Title	Arteriovenous Fistula Cannulation Group			
► Arm/Gr	oup Description:	The cannulation practices' of patie			
	verall Number of ipants Analyzed				
	sure Type: Count of Participants easure: participants				
Row Title					
	Yes	25	15.24%		
	No	139	84.76%		

Statistical analysis

The Statistical Package for Social Sciences (SPSS Inc., Chicago, IL., USA) v. 22.0 software program was used for the statistical analysis of the data from the study. The compliance with a normal distribution of the measurements obtained within the scope of the study was investigated with the "Shapiro-Wilk Test". Mean±standard deviation, median, and interquartile range (IQR) were used to present the descriptive statistics of the continuous numerical variables and number (n) and percentage (%) to present the categorical variables. Values not showing a normal distribution were compared with the "Mann-Whitney U Test" and "Kruskal-Wallis Test", while data with a normal distribution were compared with "Student's *t* Test" and "One-Way ANOVA". The homogeneity of variances was evaluated with the "Levene test". Pairwise post-hoc comparisons were made by using the "Tukey and Tmahane T2" tests in cases where there was a significant difference between the groups. Independent predictors affecting the Kt/V and URR values were investigated with logistic regression analysis using the possible factors identified with multivariate analysis previously. A p level of 0.05 was accepted as statistically significant in statistical decisions.

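### Cannulation technique was not randomised, yet the plan fixes no covariates: Kt/V and URR contrasts may be confounded by sex, body size and centre

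*Combined protocol and SAP*

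**What the plan says.** The Study Protocol calls the work a "Descriptive and cross-sectional study", while its Objective is to investigate the effect of several needling practices on dialysis adequacy. Nothing in it assigns technique to patients.

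Under Methods, treatment is partly standardised. Eligibility requires dialysis "at three days a week and four hours a day". The dialyser is common in type ("All patients were treated with a high-flux synthetic type dialyzer"), without surface area or clearance rating. Flows are given as "a dialysate flow rate 500 ml/minute and a pump speed 300-450 ml/minute", so dialysate flow is one value and pump speed a range. Patients came from "a total of four HD centers". The data form covered "questions on the patients' socio-demographic and clinical data"; the individual items are not listed.

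In the SAP, Statistical analysis, groups are compared by t test or ANOVA, or by Mann-Whitney or Kruskal-Wallis when data are not normal. For adjustment it says: "Independent predictors affecting the Kt/V and URR values were investigated with logistic regression analysis". The candidates for that model are factors found in a prior multivariate analysis. No covariate is named or always included, and centre, sex, body size and pump speed are not mentioned.

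**The concern.** Kt/V is urea clearance times treatment time, divided by urea volume. The protocol holds time constant. Pump speed, which drives clearance, and body size, which drives volume, are left free. In a non-randomised study the choice of technique may go with sex, size, access quality or local habit at a centre. A Kt/V difference between, say, antegrade and retrograde needling could then partly reflect who was needled that way and where.

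The first-line tests offer no protection against this. The logistic model protects only through covariates that were recorded, offered to the earlier analysis and selected by it. Selection on association with the outcome does not ask whether a factor is unbalanced between technique groups. What is at stake is whether a reported technique effect can be read as one.

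**Working it through.** **Inputs from the documents.** N = 164 ("The study sample consisted of 164 patients"); dialysate flow Qd = 500 ml/min; pump speed Qb = 300 to 450 ml/min; significance level 0.05. SAP Results gives direction 72 v 92, method 87/54/23, rotation 104 v 60, same line 25 v 139. Each set sums to 164 and the percentages agree. The documents give no SD, effect size, power figure or covariate distribution, so there is no stated figure to reproduce. Everything below that is marked assumed is an assumption.

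**1. Bias from sex imbalance.** Bias = difference in the proportion of men × difference in mean Kt/V between the sexes (both assumed).
- Low: 0.10 × 0.1 = 0.01.
- High: 0.30 × 0.3 = 0.09.

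**2. Bias from pump speed.** Counter-current clearance: K = Qb(e^Z − 1)/(e^Z − Qb/Qd), with Z = (KoA/Qb)(1 − Qb/Qd). KoA, the dialyser's mass-transfer coefficient, is assumed to be 800-1400 ml/min.

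| KoA | K at 300 | K at 450 | Ratio |
|---|---|---|---|
| 800 | 248 | 297 | 1.20 |
| 1400 | 280 | 353 | 1.26 |

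These ratios compare the two ends of the range. Confounding depends on the difference between group means. Take group means placed evenly around 375 ml/min and an assumed baseline Kt/V of 1.30:
- 10 ml/min apart: KoA 800 gives 1.30 × (278.4/275.2 − 1) = 0.015; KoA 1400 gives 1.30 × (325.1/320.3 − 1) = 0.02.
- 30 ml/min apart: KoA 800 gives 1.30 × (281.4/271.8 − 1) = 0.046; KoA 1400 gives 1.30 × (329.7/315.2 − 1) = 0.06.

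The range is about 0.015 to 0.06 Kt/V, and zero if the group means are equal.

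**3. Consequence for the unadjusted test.** Simulation with 72 v 92 patients, no true technique effect, and one covariate explaining 20% of the outcome variance (assumed; 4,000 runs per setting):

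| Covariate imbalance | Bias, outcome SDs | False positives, unadjusted | False positives, covariate always included |
|---|---|---|---|
| 0 | about 0 | 5% | 5% |
| 0.25 SD | 0.11 | 11% | 5% |
| 0.5 SD | 0.22 | 29% | 5% |

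**4. What a screen does.** The same simulation applied a p < 0.05 screen, as a stand-in because the SAP gives no selection rule. A recorded covariate was kept in 44-48% of runs when it explained 2% of variance, 83-85% at 5%, and at least 98% at 10% or more.

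**5. Precision.** In a linear model the SE is multiplied by √(1 − r²), where r is the joint correlation of covariates with Kt/V (assumed 0.4-0.6).
- r = 0.4: √0.84 = 0.92, an 8% cut; 1/0.84 − 1 = 19% more patients in effect.
- r = 0.6: √0.64 = 0.80, a 20% cut; 1/0.64 − 1 = 56% more.

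This does not carry over to the logistic model in the SAP. In a simulation with outcomes split at a cut-off and covariate R² of 0.1/0.3/0.5, adjustment raised the SE of the log odds ratio from 0.32 to 0.34/0.36/0.41. Power at a true difference of 0.4 SD still rose, from about 0.51-0.54 to 0.57/0.59/0.70.

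**The case against.** Four counter-arguments deserve weight.

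*No imbalance is shown.* This stands. A reader might infer that the contrasts are confounded; the documents support only that they may be. A reader might also take the 20-26% clearance difference as the bias, but that sets a patient at 300 ml/min against one at 450 and says nothing about group means.

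*A screen would keep strong determinants.* Largely right, provided they were recorded and offered. Even for weak ones the cost was small: with 2% of variance explained and 0.5 SD imbalance, false positives were 7.4% unadjusted, 5.4% after screening and 4.9% with the covariate always included. The exposure lies mainly in the unadjusted tests and in factors never offered to the screen.

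*Pump speed may be on the causal pathway.* It is tempting to say that every term in the Kt/V formula must be adjusted for. If needle placement limits achievable flow, however, adjusting for speed removes part of the effect under study. This stands and rules pump speed out of the main model.

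*The data may not be in hand.* Partly right. Sex plausibly falls under socio-demographic data, but neither weight nor individual pump speed is named as recorded, and a stated range does not prove that patient-level values were kept. Centre should be recoverable, since recruitment was by centre.

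**Conclusion.** The point holds as a weakness in the analysis rule: a question about effect in a non-randomised study is answered by unadjusted tests and a model with no guaranteed covariates. Sex, body size and centre may confound the technique contrasts.

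The magnitude cannot be determined from the documents. The illustrative biases are 0.01-0.09 Kt/V for sex and about 0.015-0.06 for pump speed. They rest on the assumed imbalances, sex difference, KoA and baseline Kt/V, and are zero without imbalance. No figure is offered for weight or centre. The 8-20% reduction in SE depends on an assumed joint correlation of 0.4-0.6 and applies only to linear models of continuous outcomes. A reader might expect narrower intervals from the planned logistic model too; the check shows otherwise.

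The change is worth making because it is inexpensive and replaces a data-driven rule with a fixed one. The documents do not show that any technique finding is wrong.

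**What to change.** Replace the covariate-selection rule in the SAP, Statistical analysis, with the following.

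1. Linear models for continuous three-month mean Kt/V and URR that always include age, sex, body weight (from the chart if it is not on the form) and centre, regardless of any screening result. Conclusions about technique rest on these models.
2. A table of these covariates, and of pump speed where available, by technique group.
3. A sensitivity model adding pump speed where patient-level values exist, stating whether it is prescribed or achieved speed. Show it beside the main model, because speed may be partly a consequence of needle placement.
4. A post hoc label. The study ran from May to December 2019 and the document, dated 20 April 2020, already contains results, so the revised models cannot be presented as pre-specified.

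The cost is SAP wording, one extra model per outcome, possible chart extraction of weight, and six degrees of freedom for the covariates (age 1, sex 1, weight 1, four centres 3). The last is modest against 164 patients, though less comfortable for contrasts involving the 23 buttonhole or 25 same-line patients.

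### The only adjusted analysis names logistic regression for continuous three-month Kt/V and URR means, with no cut-off or event and no assurance that all five practices enter the model

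*Combined protocol and SAP*

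**What the plan says.** **Outcome scale.** The Study Protocol, Methods, says how the outcomes were formed from monthly chart records: "The mean three-month Kt /V and URR values starting from the date the study was started were calculated by the researchers". A mean of monthly readings is a continuous measurement.

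**Group comparisons.** The Statistical Analysis Plan, Statistical analysis, tests normality and then chooses the comparison: "Values not showing a normal distribution were compared with the" Mann-Whitney and Kruskal-Wallis tests, and normal data by t test or one-way ANOVA. All of these are one-factor, unadjusted methods for measurements.

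**Adjusted analysis.** One sentence covers it: "Independent predictors affecting the Kt/V and URR values were investigated with logistic regression analysis using the possible factors identified with multivariate analysis previously". No threshold, event, adequacy category or ordinal grouping is given for either outcome. There is no covariate list, and the earlier multivariate step is not described. A general significance level of 0.05 follows.

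**Question.** The Objective asks about the effect on adequacy of the cannulation technique, "the direction of the fistula needle, the rotation of the needle, the AVF insertion area, and whether the artery and vein needle are on" one vascular line. That makes five practices.

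**Setting.** Patients came from "four HD centers, including one private dialysis center, one private hospital and two state hospitals in two provinces". Session schedule, dialyzer type, dialysate and needle type were common to all, but one machine setting was a range: "a dialysate flow rate 500 ml/minute and a pump speed 300-450 ml/minute".

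**The concern.** Logistic regression needs a categorical outcome, and the plan defines none. A reader cannot tell whether the fitted outcome was the mean itself, under a misnamed model, or a yes/no split at some value. With two outcomes, a split would need two cut-offs.

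The entry rule adds to the difficulty. A factor reaches the model only if an earlier analysis picked it out, so any of the five practices may be missing from the adjusted results. A practice that was screened out has no adjusted estimate, and the others were not adjusted for it.

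This matters because the practices were observed, not assigned, in four centres of different types. Practices may cluster by centre or occur together. The regression is the only specified step that could separate one practice from another, or from centre.

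**Working it through.** The documents give no power, effect size, SD, event rate or sample-size derivation, so there is no design figure to reproduce. The tabulated counts are sound: 72 + 92, 87 + 54 + 23, 104 + 60 and 25 + 139 each sum to 164.

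**Step 1. What the sentence can mean.**
- *Reading A:* logistic is a slip for linear. The means were modelled as they stand. Information lost: none.
- *Reading B:* the means were split at an unstated cut. Information is lost, and the amount depends on the cut.

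The documents do not settle which applies.

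**Step 2. Size of the loss under reading B.** Assumed, because the documents give neither: a normal outcome, and a share *p* of patients below the cut. The information kept, relative to the continuous analysis, is φ(z_p)² / [p(1 − p)] for small effects.
- p = 0.50: 0.3989² / 0.25 = 0.637; × 164 = 104
- p = 0.20: 0.2800² / 0.16 = 0.490; × 164 = 80
- p = 0.10: 0.1755² / 0.09 = 0.342; × 164 = 56

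**Step 3. The same loss as power, for one unadjusted contrast.** Needle direction is 72 antegrade against 92 retrograde. With two-sided alpha 0.05 (sidedness is not stated), the shift detectable with 80% power on the continuous scale is (1.960 + 0.842) × √(1/72 + 1/92) = 2.802 × 0.1573 = 0.441 SD. Apply that shift, with the smaller group lower, and cut the outcome so that 50%, 20% or 10% of all patients fall below. The group proportions become 0.598 v 0.423, 0.269 v 0.146 and 0.143 v 0.066. Power falls from 80% to about 60%, 50% and 38%. The 0.441 SD is only a yardstick; the documents do not give it.

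**Step 4. Can the data carry a linear model with all five practices?** Parameters: technique 2, direction 1, rotation 1, same line 1, insertion area at least 1 (its levels are not given), centre 3, and age and sex 2. The total is at least 11. 164/11 = 14.9 patients per parameter, and 164 − 12 = 152 residual degrees of freedom. If insertion area had four levels, there would be 13 parameters and 150 degrees of freedom.

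**Step 5. Price of joint adjustment.** Let R² be the share of a practice's variation explained by the other terms (not in the documents). The 95% CI half-width, in residual SDs, is 1.976 × √(1/n₁ + 1/n₂) / √(1 − R²).
- Direction (72 v 92): 1.976 × 0.1573 = 0.31 at R² = 0; 0.35 at 0.2; 0.44 at 0.5
- Same line (25 v 139): 1.976 × 0.2172 = 0.43 at R² = 0; 0.48 at 0.2; 0.61 at 0.5

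A logistic model with the same terms would pay this overlap cost as well as the loss in step 2.

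**The case against.** The strongest reply is that this is incomplete reporting, not a demonstrated error. Logistic may be a slip for linear, and multivariate may be a slip for univariate, with entry at the stated 0.05. Every loss figure depends on a cut that nobody has shown was made. The continuous group comparisons stand, and the four listed outcome measures are counts of practices that do not use this regression. The document is dated 20 April 2020, although "This study was conducted between May and December 2019", and it already contains results, so pre-specification cannot be restored. Finally, the objective is about adequacy: the odds of inadequate dialysis is a legitimate question, and a mean difference is a different estimand.

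Most of this stands, and it limits the grade and the remedy. It does not remove the point. A slip that misnames the only adjusted model still has to be corrected. If screening was univariate at 0.05, the five practices are still not assured of entry. A question about inadequate dialysis needs a stated and justified cut-off, and there is none.

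A reader might also infer that the logistic model was overfitted, with too few events per term or infinite odds ratios. The documents do not support that: a screened model may hold very few terms, and neither the terms nor the number of events is known. Nor is multiplicity across the five practices an argument here, since it arises under either model.

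**Conclusion.** The point holds as a **should-fix**. The adjusted analysis cannot be reproduced as written: the outcome scale, any cut-off and the entry rule are all unknown. Adjustment of the five practices for one another and for centre is not assured.

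The size runs from no loss of information, if the model is only misnamed, to keeping about 64%, 49% or 34% of it, if the means were split with 50%, 20% or 10% of patients below the cut. Those percentages assume normal outcomes and hold only if a split was made.

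A reader might go further and conclude that the means were in fact dichotomised, or that the study's findings are invalid. The documents establish neither.

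**What to change.** **State what was done.** Give the outcome scale actually modelled, any cut-off for Kt/V and for URR with its number of events, what the earlier multivariate analysis was, and the rule for entering factors. If logistic or multivariate is a slip, correct it.

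**Report as the main adjusted analysis**, for example:

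*Three-month mean Kt/V and three-month mean URR were each analysed by multiple linear regression. Technique, needle direction, rotation, insertion area and same vascular line were entered together regardless of univariate p-values, with centre, age and sex. Adjusted mean differences with 95% confidence intervals are given for all five practices. This analysis was revised after data collection.*

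Age and sex stand for basic patient characteristics; drop any that was not recorded. State the categories of insertion area, which has no outcome-measure entry or results table. Use robust standard errors only if residual checks call for them. If pump speed was recorded per patient, show it only in a sensitivity analysis, because it may itself depend on cannulation. A logistic analysis of inadequate dialysis may stay as secondary if its cut-off and event count are stated and justified.

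**Cost.** New wording and one re-run on data already held. Any odds ratios give way to mean differences as the main result. Intervals widen to the extent that practices overlap with centre or with each other. That overlap is unknown and is the real price.
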